# **PROTOCOL SYNOPSIS**

# Name of Sponsor/Company:

NantBioScience, Inc.

#### Name of Investigational Product:

Ad5 [E1-, E2b-]-HER2/neu Vaccine, Suspension for Injection (ETBX-021)

#### Name of Active Ingredient:

Ad5 [E1-, E2b-]-HER2/neu

#### Title of Study:

Phase I Study of Ad5 [E1-, E2b-]-HER2/neu Vaccine (ETBX-021) in Subjects with Unresectable Locally Advanced or Metastatic HER2-Expressing Breast Cancer

#### Study Number:

CMS-005

#### **Study Phase:**

Phase I

#### Primary Objectives:

• Determine the overall safety and recommended phase 2 dose of ETBX-021 when administered subcutaneously (SC) every 3 weeks for three injections followed by three booster injections at 3-month intervals to subjects with HER2-expressing breast cancer.

## **Secondary Objectives:**

• Make preliminary assessments of objective response rate (ORR), disease control rate (DCR), duration of response, progression-free survival (PFS), and overall survival (OS) in subjects with HER2-expressing breast cancer treated with ETBX-021.

## **Exploratory Objectives:**

• Evaluate the immunogenicity of ETBX-021 and determine the genomic and proteomic profile of subjects' tumors to identify gene mutations, gene amplifications, RNA-expression levels, and protein-expression levels. Correlations between genomic/proteomic profiles and efficacy outcomes will be assessed.

## **Primary Endpoints:**

- Dose-limiting toxicities (DLTs) and maximum tolerated dose (MTD) or highest tested dose (HTD).
- Treatment-emergent adverse event (AEs) and serious adverse events (SAEs).
- Clinically significant changes in safety laboratory tests, physical examinations, electrocardiograms (ECGs), left ventricular ejection fraction (LVEF), and vital signs.

## **Secondary Endpoints:**

- ORR (confirmed complete or partial response) according to the Response Evaluation Criteria in Solid Tumors (RECIST) Version 1.1.
- DCR (confirmed response or stable disease lasting for at least 6 months).
- Duration of response.
- PFS.
- OS.

# **Exploratory Endpoints:**

- Immunogenicity of ETBX-021 by flow cytometric analysis of T-cell frequency, activation status, cytokine profiles, and antibody levels.
- Genetic and proteomic profiling and correlates with efficacy.

# **Study Design:**

This is a Phase I trial in subjects with unresectable locally advanced or metastatic HER2-low expressing (IHC 1+ or 2+) breast cancer. The study will be conducted in two parts: the first part will involve dose escalation using a 3 + 3 design, and the second part will involve the expansion of the MTD or HTD to further evaluate safety, preliminary efficacy, and immunogenicity. In the first part, 3 to 6 subjects will be sequentially enrolled starting at dose cohort 1. Subjects will be assessed for dose-limiting toxicities (DLTs).

- Cohort 1:  $5 \times 10^{10}$  virus particles (VP).
- Cohort 2: 5 x 10^11 VP.
- If needed, dose de-escalation cohort (cohort -1):  $5 \times 10^9$  VP.

Dose expansion will occur when the MTD or HTD has been determined. An additional 12 subjects will be enrolled in the dose expansion component of the trial, for a total of 18 subjects at the MTD or HTD.

# **Enrollment (planned):**

Up to 30 subjects will be enrolled in the study. In the dose escalation component, 3 to 6 subjects will be sequentially enrolled starting at Cohort 1. In the dose expansion component (i.e., once the MTD or HTD has been identified), an additional 12 subjects will be enrolled for a total of 18 subjects in the MTD/HTD cohort to obtain further safety, preliminary efficacy, and immunogenicity data.

# Diagnosis and Main Criteria for Inclusion:

Subjects must have histologically confirmed unresectable locally advanced or metastatic breast cancer that expresses HER2 (IHC 1+ or 2+). Subjects with HER2 IHC 3+ tumors are excluded.

# Investigational Product, Dosage, and Mode of Administration:

ETBX-021 (5 x  $10^9$ , 5 x  $10^{10}$ , or 5 x  $10^{11}$  VP in 1.0 mL) will be administered by SC injection every 3 weeks for 3 injections, followed by 3 booster injections at 3-month intervals.

## **Duration of Treatment:**

Subjects will receive treatment for up to 42 weeks (injections at 0, 3, and 6 weeks with booster injections at 18, 30, and 42 weeks) or until they experience progressive disease or unacceptable toxicity, withdraw consent, or if the Investigator feels it is no longer in their best interest to continue treatment.

## **Reference Therapy, Dosage, and Mode of Administration:**

Not applicable.

# Criteria for Evaluation:

**Safety:** Safety endpoints include assessments of DLT, MTD or HTD, treatment-emergent AEs, SAEs, and clinically significant changes in safety laboratory tests, physical examinations, ECGs, LVEF, and vital signs. Toxicities will be graded using the National Cancer Institute (NCI) Common Terminology Criteria for Adverse Events (CTCAE) Version 4.03.

**Efficacy:** Tumor response (ORR and DCR) will be evaluated according to RECIST Version 1.1; duration of response, PFS, and OS will also be evaluated.

**Exploratory Immune Analysis:** Immune responses will be detected and quantified in flow cytometrybased and serum assays. **Exploratory Molecular Profiling and Analysis:** Genomic sequencing of tumor cells relative to nontumor cells to identify the genomic variances that may contribute to response or disease progression and provide an understanding of molecular abnormalities; RNA sequencing to provide expression data and give relevance to DNA mutations; and quantitative proteomics to determine the exact amounts of specific proteins and to confirm expression of genes predictive of response and disease progression.

# **Statistical Methods:**

The rate of DLTs and the MTD or HTD will be assessed. Overall safety will be assessed by descriptive analyses using tabulated frequencies of AEs by grade using CTCAE Version 4.03 within dose cohorts and for the overall study population in terms of treatment-emergent AEs, SAEs, and clinically significant changes in safety laboratory tests, physical examinations, ECGs, LVEF, and vital signs. ORR and DCR will be evaluated according to RECIST Version 1.1 by dose cohort and overall; duration of response will also be evaluated. PFS and OS will be analyzed using Kaplan-Meier methods by dose cohort and overall.

# Figure 1: Study Design and Treatment Schema

# Table 3:Time and Events Schedule

Assessment	Screening	Baseline	(Eve	TreatmentBoosters(Every 3-Week Dosing)(Every 3-Month Dosing)							End of Study	Post Study Follow Up		
Study Week	Day -28 to -7	Day -7 to 1	0	3	6	9	18	21	30	33	42	45		
Clinic Visit	X	Х	X	X	Х	Х	Х		Х		Х		X	
Informed Consent	X													
Inclusion/Exclusion	Х	Х												
Demographics	X													
Physical Examination, Height a , Weight, ECOG	X	Х	X	X	X	Х	X		X		X		Х	
Medical History b	X	Х												
Confirm HER2 Expression	X													
Concomitant Medications	X	Х	X	X	Х	Х	Х		Х		X		Х	
Vital Signs c	X	Х	X	X	Х	Х	Х		Х		X		Х	
12-Lead ECG	X					Х	Х		Х		X		X	
Echocardiogram/MUGA d	X					Х	Х		Х		X		Х	
Confirm Contraceptive Measures e	X													
Study Drug Injection/ Injection Site Reaction Monitoring f			X	X	X		X		X		Х			
Dispensation of Subject Diary Card g			X	X	X		X		X		X			
Review of Subject Diary Card g				X	X	X		X		X		X		

# ETBX-021 Clinical Trial Protocol: CMS-005

Assessment	Screening	Baseline	ne Treatment (Every 3-Week Dosing) Boosters (Every 3-Month Dosing)							End of Study	Post Study Follow Up			
Study Week	Day -28 to -7	Day -7 to 1	0	3	6	9	18	21	30	33	42	45		
Telephone Contact 72 Hours Post Injection			X	X	X		X		X		X			
Tumor Imaging h		X				Х		Х		Х		Х	X	
Pregnancy Test i	Х		X	Х	Х		Х		Х		Х		X	
Urinalysis	Х					Х			Х				X	
Chemistry Panel	Х	Х	X	Х	Х	Х	Х		Х		Х		X	
CBC, Differential, Platelets	Х	Х	X	X	X	X	X	X	X	Х	X	X	X	
Coagulation	Х					Х					Х		X	
Serum Virology (HIV, HBV, HCV)	X													
Adverse Events		Х	X	Х	Х	Х	Х	Х	Х	Х	Х	Х	X	
Exploratory Immune Analysis		Х	X	Х	Х	Х	Х	Х	Х	Х	Х	Х		
Exploratory Genomics and Proteomics Molecular Analysis		X												
Telephone Follow Up j														X

# **PROTOCOL SYNOPSIS**

# Name of Sponsor/Company:

NantBioScience, Inc.

## Name of Investigational Product:

Ad5 [E1-, E2b-]-HER2/neu Vaccine, Suspension for Injection (ETBX-021)

#### Name of Active Ingredient:

Ad5 [E1-, E2b-]-HER2/neu

#### Title of Study:

Phase I Study of Ad5 [E1-, E2b-]-HER2/neu Vaccine (ETBX-021) in Subjects with Unresectable Locally Advanced or Metastatic HER2-Expressing Breast Cancer

#### Study Number:

CMS-005

## Study Phase:

Phase I

#### **Primary Objectives:**

• Determine the overall safety and recommended phase 2 dose of ETBX-021 when administered subcutaneously (SC) every 3 weeks for three injections followed by three booster injections at 3-month intervals to subjects with HER2-expressing breast cancer.

# **Secondary Objectives:**

• Make preliminary assessments of objective response rate (ORR), disease control rate (DCR), duration of response, progression-free survival (PFS), and overall survival (OS) in subjects with HER2-expressing breast cancer treated with ETBX-021.

## **Exploratory Objectives:**

• Evaluate the immunogenicity of ETBX-021 and determine the genomic and proteomic profile of subjects' tumors to identify gene mutations, gene amplifications, RNA-expression levels, and protein-expression levels. Correlations between genomic/proteomic profiles and efficacy outcomes will be assessed.

#### **Primary Endpoints:**

- Dose-limiting toxicities (DLTs) and maximum tolerated dose (MTD) or highest tested dose (HTD).
- Treatment-emergent adverse event (AEs) and serious adverse events (SAEs).
- Clinically significant changes in safety laboratory tests, physical examinations, electrocardiograms (ECGs), left ventricular ejection fraction (LVEF), and vital signs.

## **Secondary Endpoints:**

- ORR (confirmed complete or partial response) according to the Response Evaluation Criteria in Solid Tumors (RECIST) Version 1.1.
- DCR (confirmed response or stable disease lasting for at least 6 months).
- Duration of response.
- PFS.

#### • OS.

# **Exploratory Endpoints:**

- Immunogenicity of ETBX-021 by flow cytometric analysis of T-cell frequency, activation status, cytokine profiles, and antibody levels.
- Genetic and proteomic profiling and correlations with efficacy.

# Study Design:

This is a Phase I trial in subjects with unresectable locally advanced or metastatic HER2-low expressing (IHC 1+ or 2+) breast cancer. The study will be conducted in two parts: the first part will involve dose escalation using a 3 + 3 design, and the second part will involve the expansion of the MTD or HTD to further evaluate safety, preliminary efficacy, and immunogenicity. In the first part, 3 to 6 subjects will be sequentially enrolled starting at dose cohort 1. Subjects will be assessed for dose-limiting toxicities (DLTs).

- Cohort 1:  $5 \times 10^{10}$  virus particles (VP).
- Cohort 2: 5 x 10^11 VP.
- If needed, dose de-escalation cohort (cohort -1):  $5 \times 10^9$  VP.

Dose expansion will occur when the MTD or HTD has been determined. An additional 12 subjects will be enrolled in the dose expansion component of the trial, for a total of 18 subjects at the MTD or HTD.

# **Enrollment (planned):**

Up to 30 subjects will be enrolled in the study. In the dose escalation component, 3 to 6 subjects will be sequentially enrolled starting at Cohort 1. In the dose expansion component (i.e., once the MTD or HTD has been identified), an additional 12 subjects will be enrolled for a total of 18 subjects in the MTD/HTD cohort to obtain further safety, preliminary efficacy, and immunogenicity data.

# Diagnosis and Main Criteria for Inclusion:

Subjects must have histologically confirmed unresectable locally advanced or metastatic breast cancer that expresses HER2 (IHC 1+ or 2+). Subjects with HER2 IHC 3+ tumors are excluded.

## Investigational Product, Dosage, and Mode of Administration:

ETBX-021 (5 x  $10^9$ , 5 x  $10^{10}$ , or 5 x  $10^{11}$  VP in 1.0 mL) will be administered by SC injection every 3 weeks for 3 injections, followed by 3 booster injections at 3-month intervals.

## **Duration of Treatment:**

Subjects will receive treatment for up to 42 weeks (injections at 0, 3, and 6 weeks with booster injections at 18, 30, and 42 weeks) or until they experience progressive disease or unacceptable toxicity, withdraw consent, or if the Investigator feels it is no longer in their best interest to continue treatment.

## Reference Therapy, Dosage, and Mode of Administration:

Not applicable.

## Criteria for Evaluation:

**Safety:** Safety endpoints include assessments of DLT, MTD or HTD, treatment-emergent AEs, SAEs, and clinically significant changes in safety laboratory tests, physical examinations, ECGs, LVEF, and vital signs. Toxicities will be graded using the National Cancer Institute (NCI) Common Terminology Criteria for Adverse Events (CTCAE) Version 4.03.

**Efficacy:** Tumor response (ORR and DCR) will be evaluated according to RECIST Version 1.1; duration of response, PFS, and OS will also be evaluated.

**Exploratory Immune Analysis:** Immune responses will be detected and quantified in flow cytometrybased and serum assays.

**Exploratory Molecular Profiling and Analysis and its Rationale:** Genomic sequencing of tumor cells from tissue relative to non-tumor cells from whole blood will be profiled to identify the genomic variances that may contribute to response or disease progression and provide an understanding of molecular abnormalities. RNA sequencing will be conducted to provide expression data and give relevance to DNA mutations. Quantitative proteomics analysis will be conducted to determine the exact amounts of specific proteins and to confirm expression of genes that are correlative of response to vaccine immunotherapy and disease progression. All genomic, transcriptomic, and proteomic molecular analyses will be retrospective and exploratory.

#### **Statistical Methods:**

The rate of DLTs and the MTD or HTD will be assessed. Overall safety will be assessed by descriptive analyses using tabulated frequencies of AEs by grade using CTCAE Version 4.03 within dose cohorts and for the overall study population in terms of treatment-emergent AEs, SAEs, and clinically significant changes in safety laboratory tests, physical examinations, ECGs, LVEF, and vital signs. ORR and DCR will be evaluated according to RECIST Version 1.1 by dose cohort and overall; duration of response will also be evaluated. PFS and OS will be analyzed using Kaplan-Meier methods by dose cohort and overall.

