## **Secondary Endpoints:**

- ORR (confirmed complete or partial response) according to the Response Evaluation Criteria in Solid Tumors (RECIST) Version 1.1.
- DCR (confirmed response or stable disease lasting for at least 6 months).
- Duration of response.
- PFS.
- OS.

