# Study Design:

This is a phase 1 trial in subjects with unresectable locally advanced or metastatic HER2-expressing (IHC 1+, 2+, or 3+) cancer. The study will be conducted in two parts: the first part will involve dose escalation using a 3 + 3 design, and the second part will involve the expansion of the MTD or HTD to further evaluate safety, preliminary efficacy, and immunogenicity. In the first part, 3 to 6 subjects will be sequentially enrolled starting at dose cohort 1. Subjects will be assessed for dose-limiting toxicities (DLTs).

- Cohort 1:  $5 \times 10^{10}$  virus particles (VP).
- Cohort 2:  $5 \times 10^{11}$  VP.
- If needed, dose de-escalation cohort (cohort -1):  $5 \times 10^9$  VP.

Dose expansion will occur when the MTD or HTD has been determined. An additional 12 subjects will be enrolled in the dose expansion component of the trial, for a total of 18 subjects at the MTD or HTD.

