# Enrollment (planned):

Up to 30 subjects will be enrolled in the study. In the dose escalation component, 3 to 6 subjects will be sequentially enrolled starting at cohort 1. In the dose expansion component (ie, once the MTD or HTD has been identified), an additional 12 subjects will be enrolled for a total of 18 subjects in the MTD/HTD cohort to obtain further safety, preliminary efficacy, and immunogenicity data.

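### Tumor response is analyzed only as yes/no ORR and DCR; adding ranked percent change in tumor size as a supplementary outcome would give the molecular correlations more information at little cost

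*Combined protocol and SAP*

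**What the plan says.** References are to the Amendment 4 synopsis, the latest in the file. The response sentence under Statistical Methods is worded the same in all five synopses.

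- **Secondary Endpoints** defines the two rates as "ORR (confirmed complete or partial response) according to the Response Evaluation Criteria in Solid Tumors (RECIST) Version 1.1" and "DCR (confirmed response or stable disease lasting for at least 6 months". Each subject counts as yes or no. Duration of response, PFS and OS are also listed.
- **Statistical Methods** says "ORR and DCR will be evaluated according to RECIST Version 1.1 by dose cohort and overall; duration of response will also be evaluated", and puts PFS and OS under Kaplan-Meier, by cohort and overall.
- **Exploratory Objectives** says "Correlations between genomic/proteomic profiles and efficacy outcomes will be assessed". Criteria for Evaluation gives one purpose of the proteomics as "to confirm expression of genes that are correlative of response to vaccine immunotherapy and disease progression", and describes all the molecular work as retrospective and exploratory. No method, sample size or power is given for the correlations.
- **Size:** "In the first part, 3 to 6 subjects will be sequentially enrolled starting at dose cohort 1"; then 12 more, "for a total of 18 subjects at the MTD or HTD". Overall, "Up to 30 subjects will be enrolled in the study".
- **Time and Events Schedule (Table 3)** places tumor imaging at screening, weeks 9, 18, 30 and 42, and End of Study.

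**The concern.** RECIST 1.1 judges partial response, and progression in target lesions, from the sum of target-lesion diameters. In subjects with measurable disease the trial should therefore hold a continuous tumor measurement at each scan. The synopsis reports response only after that measurement has been cut into two classes.

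In a cohort of 18, a low response rate leaves few or no responders. With none, no association between a marker and ORR can be estimated. With one, a rank test against ORR cannot reach the usual threshold. The part of the exploratory objective that concerns response would then rest on DCR and on the time-to-event outcomes. The measured shrinkage or growth would go unused as a graded outcome, although it needs no further scan.

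**Working it through.** **The plan's own figures.** 6 escalation subjects + 12 expansion subjects = 18 at the MTD or HTD. Three cohorts of 6, plus 12, gives 30. Both stated sizes reproduce. The documents give no power, precision or expected response rate for ORR, DCR or the correlations, so the rates below are assumptions shown as a range.

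**Chance of 0 or 1 responder.** P = (1−p)^n + n·p·(1−p)^(n−1).

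- n=18, p=0.05: 0.397 + 0.376 = 0.774
- n=18, p=0.10: 0.150 + 0.300 = 0.450
- n=18, p=0.20: 0.018 + 0.081 = 0.099
- n=30, same three rates: 0.554, 0.184, 0.011

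**Smallest attainable p-value.** For an exact two-sided rank test of a continuous marker with k responders, the minimum is 2/C(n,k). With k=1 this is 2/18 = 0.11 or 2/30 = 0.067, so 0.05 is out of reach at either size. For a yes/no marker under Fisher's exact test, the minimum with one responder is 1/18 = 0.056 or 1/30 = 0.033, reached only if the responder is the sole marker-positive subject. If the marker splits 18 subjects 9 and 9, significance needs at least 5 responders, all in one group: 2·C(9,5)/C(18,5) = 252/8568 = 0.029.

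**Power for a single marker.** Simulation with 4,000 runs per setting. Marker and tumor change are bivariate normal with correlation r, and every subject is measurable. The yes/no outcome is the lowest fraction of tumor change equal to the assumed rate. Tests are two-sided at 5% without multiplicity adjustment: Spearman for continuous change, exact Mann-Whitney for the yes/no outcome. Figures are approximate, with r=0.6.

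| Outcome used | n=18 | n=30 |
|---|---|---|
| Continuous change | 71% | 93% |
| Yes/no, rate 5% | 7% | 21% |
| Yes/no, rate 10% | 18% | 39% to 41% |
| Yes/no, rate 20% | 36% | 62% |
| Yes/no, rate 30% to 40% (possible DCR) | 45% to 48% | 73% to 78% |

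The DCR row is a simplification, because DCR also depends on stable disease lasting 6 months.

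**Sensitivity.**

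- At r=0.3 and n=18, continuous change gives only about 21%.
- At r=0.6 and n=18, with a Bonferroni correction for an assumed 1,000 markers, it gives about 5%.
- With about 30% of subjects tied at the worst rank, power at r=0.6 and n=18 stays near 69%.
- A different model points the same way. A marker splitting 18 subjects equally, with a 1 SD difference in tumor change, gives 51% with a t-test, against 0.1%, 0.9% or 8% with Fisher's test at ORR 5%, 10% or 20%.

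**The case against.** A reader might infer that the trial cannot relate the molecular profiles to outcome at all. The documents do not support that. The objective names efficacy outcomes in general, and these include DCR, duration of response, PFS and OS. PFS already uses the serial scans as a graded outcome, and Criteria for Evaluation names disease progression beside response. The limit with 0 or 1 responder applies to ORR only. Nor would the dose cohorts be described by a responder count alone, since DCR, PFS and OS are also reported by cohort.

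Four further points stand.

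- **The low ORR is assumed.** At 20%, 0 or 1 responder is unlikely, and nothing confines the correlations to 18 of the possible 30 subjects.
- **Week-9 change is no cleaner than PFS.** In a single arm, a marker correlated with either may be prognostic and say nothing about the vaccine. Preferring tumor change on that ground would be inconsistent.
- **The power gain is for one strong marker.** Continuous change does not rescue a genome-wide search at this size.
- **Absence and measurement are both inferred.** Only synopses and schedules are available, and the imaging footnote is not shown. A percent-change analysis may be planned elsewhere. That sums are recorded at every scan follows from RECIST 1.1 and the imaging row; the text does not state it, and no visible criterion requires measurable disease.

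These points lower the severity. They do not remove the loss of information when tumor change is cut into two classes: at r=0.6 and n=18, continuous change has more power than a cut at any rate shown above.

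**Conclusion.** The point holds as an optional, cheap improvement. The current synopsis analyzes tumor response only as two yes/no rates, beside duration of response, PFS and OS, and lists no continuous tumor-size outcome. If the true ORR is 5% to 10%, the 18-subject cohort has 0 or 1 responder 77% to 45% of the time, and ORR then supports no useful marker correlation. For one marker correlated 0.6 with tumor change, continuous change raises power with 18 subjects to about 71%. The yes/no comparators give 7% to 36% over ORR 5% to 20%, and 45% to 48% at a disease-control rate of 30% to 40%.

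These figures rest on an assumed response rate, one assumed correlation, no multiplicity adjustment and full measurability. At r=0.3 the power is about 21%, so the molecular work stays hypothesis-generating either way. Efficacy is a preliminary, secondary aim here, and nothing in this point affects the safety or dose objective.

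**What to change.** Add to Statistical Methods, as a supplementary exploratory outcome:

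> Percent change from baseline in the sum of target-lesion diameters at week 9, and best percent change, will be shown per subject (waterfall plot) and summarised by dose cohort with median and range. A 95% confidence interval for the median will be given only where n is at least 6 (the MTD/HTD cohort and overall). Subjects with progression by any route, including new lesions, or death by week 9 are given the worst rank whether or not a week-9 sum is available. The ranked week-9 change will be used alongside ORR, DCR, PFS and OS in the genomic and proteomic correlations.

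ORR and DCR stay unchanged, and the correlation with response that the plan names is kept. The limit of 6 is needed because the widest distribution-free interval for a median has coverage 1 − 2·(1/2)^n: 75% at n=3, 94% at n=5 and 97% at n=6. The worst-rank rule must cover new-lesion progression; otherwise a subject whose target lesions shrink while new ones appear would rank as favorable. The text should also say how a subject with no week-9 sum and neither progression nor death is handled, and report how many there are.

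The cost is wording and a few extra outputs, with no new visit or scan. Subjects without measurable disease contribute only through the worst-rank rule. A correlation with tumor change, as with PFS, cannot separate prognostic from vaccine-related markers in a single arm.
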